AMD, at its early stages, presents with drusen and abnormalities of retinal pigment epithelium (RPE). As the disease progresses with age to the advanced stage, it generally progresses to either the non-neovascular (“atrophic, dry”) form of AMD or the neovascular (“wet or exudative”) form of the disease (Mitchell et. al., 2018). In the dry, atrophic form, loss of photoreceptors, RPE cells and associated capillaries (choriocapillaris) in the macula result in marked thinning and/or atrophy of retinal tissue. This collective phenotype in the advanced stage of dry AMD is termed geographic atrophy (GA) (Holz et al, 2014). Furthermore, development or progression of geographic atrophy over time is a common cause of vision loss in patients diagnosed with the wet form of advanced AMD who are treated with anti-VEGF therapy, indicating that in many patients regardless of having the dry or the wet form of AMD, the final anatomic outcome leading to loss of vision is geographic atrophy (Bhisitkul et al., 2015; Grunwald et al., 2017; Abdelfatah et al., 2016).

Geographic atrophy is a significant cause of bilateral, irreversible and severe loss of functional vision, with a potential loss on average of 22 letters over 5 years, and is associated with a major impact on functional vision, quality of life, and independence (Mitchell et al., 2018;

Sivaprasad et al., 2019; Boyer et al. 2017, AREDS Report Number 26, 2009). The median time for development of central geographic atrophy from the time of diagnosis is 2.5 years with an expectancy of development in the fellow eye in approximately 7 years (AREDS Report Number 26, 2009).

Although anti-VEGF therapy is available for treatment of wet AMD, currently no Food and Drug Administration (FDA) or European Medicines Agency (EMA) approved treatment is available for geographic atrophy (Brown et al., 2006; Rosenfeld et al, 2006; Heier et al., 2012; Martin et al., 2012; Boyer et al. 2017).

The absence of treatment options for geographic atrophy secondary to AMD represents an area of urgent unmet medical need and a major public health concern for the rapidly increasing elderly population.

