4.3.4 Study OPH2003

A pivotal international, multicenter, randomized, double-masked, Sham-controlled clinical trial was performed to evaluate the safety and efficacy of Zimura in patients with geographic atrophy secondary to AMD. [REDACTED]

[REDACTED]

In Part 1 of the trial: [REDACTED] patients were randomized to receive monthly intravitreal injections of Zimura 1 mg; [REDACTED] Zimura 2 mg; and [REDACTED] Sham injections.

This trial was modified (while masked) to include a 4 mg dose group and therefore part 2 was added. In Part 2 of the trial: [REDACTED] patients were randomized to receive monthly intravitreal injections of Zimura 4 mg, administered as two injections of Zimura 2 mg; [REDACTED] Zimura 2 mg plus a Sham injection; and [REDACTED] Sham injections, administered as two separate Sham injections.

[REDACTED]

[REDACTED]

Safety

Zimura was generally well tolerated after 12 months of administration and there were no Zimura-related AEs, no Zimura-related inflammation, and no Zimura-related discontinuations. Further, there have been no ocular serious adverse events and no cases of endophthalmitis reported in the study eye in this clinical trial. During the first 12 months of the trial, the incidence of choroidal neovascularization (CNV) in the untreated fellow eye was 10 patients (3.5%); in the study eye of the Sham control group was 3 patients (2.7%); in the Zimura 2 mg group was 6 patients (9.0%); and in the Zimura 4 mg group was 8 patients (9.6%). These numbers were lower than reported in the literature for complement C3 inhibition (Liao et al., 2019). The most frequently reported ocular adverse events were related to the injection procedure.

Primary Efficacy Endpoint

The prespecified primary efficacy endpoint, mean rate of change in GA growth over 12 months, was measured by fundus autofluorescence (FAF) based on readings at three time points (Baseline, Month 6, and Month 12) and was calculated using the square root transformation of the GA area. The FAF images were assessed by an independent masked reading center. This trial met its prespecified primary efficacy endpoint.

The reduction in the mean rate of GA growth over 12 months was 27.38% ($p = 0.0072$) for the Zimura 2 mg group as compared to the corresponding Sham control group, and 27.81% ($p = 0.0051$) for the Zimura 4 mg group as compared to the corresponding Sham control group. These efficacy data for both dose groups were similar and statistically significant. [REDACTED]

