The primary analysis will use the ITT population and will be based on a Mixed Model for Repeated Measures (MMRM) to compare the treatment groups. This analysis provides valid estimates as long as the missing data mechanism fulfills the Missing at Random (MAR) assumption. However, sensitivity analyses (see Section 7.4.1) will be performed to assess the potential magnitude and direction of the impact of missing data.

CONTROL OF ALPHA

The overall (one-sided) false positive error rate in this trial is 0.025.

An alpha-level adjustment will be made in the assessment of statistical significance at the time of the final analysis, equal to (two-sided) 0.001 for each DSMB meeting for any look at the data. There will not be formal interim analyses for early termination for benefit and, in turn, the DSMB will not make recommendations for early termination even if emerging data would provide strongly favorable evidence for benefit. Rather, the principal justification for the DSMB to have access to emerging data on efficacy as well as safety data during DSMB meetings is to enable the DSMB to more effectively safeguard interests of study participants through a properly informed assessment of benefit-to-risk.

ANALYSIS OF PRIMARY EFFICACY OUTCOME

The primary efficacy endpoint is the mean rate of growth (slope) estimated based on GA area measured by FAF in at least 3 time points: Baseline, Month 6, and Month 12 (square root transformation). To eliminate the dependency of GA growth rates on the Baseline lesion size (Feuer et al., 2013), instead of using the observed GA area measurement, the square root of the GA area will be used in the analysis.

Primary Estimand

In alignment with the primary objective of the study, the main estimand to be used for the evaluation of the primary outcome is described as:

The difference in the mean rate of growth (slope) estimated based on GA area measured by FAF in at least 3 time points: Baseline, Month 6, and Month 12 (square root transformation) between treatment conditions (Zimura versus Sham) in the target patient population, regardless of any non-adherence to or interruption of study treatment, and regardless of initiation of alternative treatment.

The following 5 attributes define the main estimand for primary endpoint evaluation:

A. Population:

CONFIDENTIAL

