- █ [REDACTED]
- █ [REDACTED]
- █ [REDACTED]
- █ [REDACTED]
- █ [REDACTED]

SENSITIVITY ANALYSES

Sensitivity Analyses for Missing Data

For the analyses of the primary outcome, the MMRM analysis does not require data imputation and uses only the observed data. Moreover, assuming that the missing data are MAR, the model yields valid results that are comparable to those obtained by applying MI under the MAR assumption.

Four analyses described by Miller et al. (2001) will be performed for further insight into the potential impact of missing data on the results:

1. the observed means from the active arm and the sham arm will be imputed to patients with missing data in the arm they were allocated to;
2. the average of observed means from the active arm and the sham arm will be imputed to all patients with missing data;
3. the observed mean from the sham arm will be imputed to all patients with missing data.
4. the observed means from the active arm and the sham arm will be imputed to patients with missing data in the opposite arm they were allocated to (a “cross-over” scheme);

These four sensitivity analyses make different assumptions about missing data, and are likely to be increasingly biased against a true treatment effect. A robust treatment effect would be expected to remain statistically significant in analyses 1 to 3, since these are likely to be much less biased than analysis 4 under the assumption of a true treatment effect.

To check the sensitivity of the results of the primary efficacy analysis (using the primary estimator as described in section 7.2) to the MAR assumption, MI based on models compatible with Missing Not At

CONFIDENTIAL

Random (MNAR) missingness mechanisms will be used. Two approaches, using SAS' PROC MI, will be considered:

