1. The “shift imputation” approach: for missing values at a particular visit, it will be assumed that their expected value is smaller (shifted) by a specified amount (i.e., a specified shift in the size of GA), than for the observed responses (implying that the missing values are more likely corresponding to smaller changes vs. Baseline than the observed ones). Increasing values of the shift will be explored to investigate the sensitivity of the results. This approach can be applied to data with arbitrary missing data patterns. The “tipping point” is the value of the shift that causes statistical significance to be lost. For a robust treatment effect, the tipping point would be considered an implausible value of the shift used in the missing data imputation.

2. The “pattern-mixture-model imputation” approach: missing values at Month 12 visit will be imputed by using the pattern-mixture-model restrictions. Pattern-mixture models provide a general and flexible framework for sensitivity analyses that allows formulating assumptions regarding missing data in a transparent and clinically interpretable manner. In particular, Complete-Case Missing Value (CCMV) and Neighbouring-Case Missing Value (NCMV) restrictions will be applied.

Of note, these imputation techniques are known to induce potential bias, hence they will be used only for sensitivity purposes.

Sensitivity Analysis for Stratification Error

On Monday November 16, 2020 the Duke Reading Center notified that an error occurred at the reading center in the reporting of fundus autofluorescence (FAF) results used as stratification factors for randomization of eligible patients into GATHER2 (ISEE2008) clinical trial.

As a result, 38 patients randomized with Baseline geographic atrophy size between 4 to 10 mm² were placed in a stratum that included participants with size ≥ 10 mm² rather than being placed in stratum that included participants with size < 10 mm².

To assess the impact of this stratification error, two sensitivity analyses will be done by performing analyses that stratify by 3-level covariates for the Baseline geographic atrophy size. The first analysis will stratify by: < 4 mm² vs. ≥ 4 to < 10 mm² vs. ≥ 10 mm², and the second analysis will stratify by: patients randomized prior to November 16, 2020 vs. < 4 mm² vs. ≥ 4 mm².

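### The Year 1 tipping-point analysis shifts missing GA values toward less growth, the better outcome, and names no arm, so a large tipping point does not show robustness to worse outcomes on Zimura

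*SAP*

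**What the plan says.** The Efficacy Evaluation section of the Year 1 SAP says that sensitivity analyses "will be performed to assess the potential magnitude and direction of the impact of missing data". Under Sensitivity Analyses for Missing Data, two multiple-imputation approaches are meant to test the MAR assumption. The first is shift imputation. For a missing value at a visit, "it will be assumed that their expected value is smaller (shifted) by a specified amount", which the SAP explains as "implying that the missing values are more likely corresponding to smaller changes vs. Baseline than the observed ones". The shift is increased until significance is lost, and that value is the tipping point. The reading rule is: "For a robust treatment effect, the tipping point would be considered an implausible value of the shift used in the missing data imputation".

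No arm is named, and the size of the shift has no unit. The visible text of this item carries no redaction marks.

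The same section lists four single-value imputations. In the third, "the observed mean from the sham arm will be imputed to all patients with missing data". The fourth swaps the arm means. The SAP expects a robust effect to stay significant in the first three.

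Year 2 SAP 4.2.1.3.2 also plans a tipping-point analysis. It gives neither arm nor direction and refers to an appendix of the primary-analysis study report.

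**The concern.** Zimura is meant to slow GA growth, so a smaller change from Baseline is the favourable outcome. A tipping-point analysis should ask how much worse treated patients with missing data would have to be before the conclusion fails. This one makes patients with missing data better. The parenthetical explanation repeats the direction, so a single mistyped word does not account for it.

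Because no arm is named, the effect on the treatment contrast is undefined:

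- **Both arms, equal missingness:** the shift cancels in the estimate.
- **Both arms, more missing on Zimura:** the shift favours the drug.
- **Zimura alone:** it cannot tip.
- **Sham alone, or both arms with more missing on Sham:** it works against the drug.

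The direction also makes the reading rule easy to satisfy. A downward shift larger than a year's growth implies that the imputed lesions ended smaller than at Baseline, so a large tipping point looks implausible whatever happened to Zimura patients with missing data. A reader could then take a favourable result as protection against a risk that was not examined.

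**Working it through.** **Inputs from the documents.** About 400 patients, 1:1, so 200 per arm. Design effect 0.11 mm, smallest significant estimate 0.057 mm, and 97% power at two-sided 0.05 (Protocol 11.3). Nearly 90% power at two-sided 0.01 (Year 1 SAP, Study Design and Sample Size). Reduction of 27.38% for 2 mg in OPH2003 (Protocol 4.3.4).

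**Assumptions.** No SD is given, so it is back-solved. No missing-data rate is given, so 5% to 15% per arm is used. The shift is taken on the square-root (mm) scale. Yearly growth stands in for the model slope.

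**Reproducing the plan's figures.** SD = (0.057/1.96)/√(2/200) = 0.291. Power for 0.11 mm is then Φ(0.11/0.0291 − 1.96) ≈ 97%, and about 89% at 0.01. Both agree with the plan. This shows that the stated figures are consistent with each other; it is not independent evidence for the SD. SD 0.29 is used below.

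**Growth scale.** Sham 0.11/0.2738 ≈ 0.40 mm/year; Zimura 0.40 − 0.11 ≈ 0.29 mm/year.

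**Formula.** Let mZ and mS be the missing fractions, and dZ and dS the shifts toward larger growth (negative under the SAP's wording).

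- Estimate = effect − mZ·dZ + mS·dS
- Variance = Σ over arms of [SD²/(1−m) + m(1−m)d²]/200
- Tipping point = smallest shift at which estimate/SE falls below 1.96

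Example, 10%/10%, unshifted: SE = √(2 × 0.0841/0.9/200) = 0.0306, z = 0.11/0.0306 = 3.60. With both arms down 0.4 mm, the estimate is 0.11 + 0.04 − 0.04 = 0.11, SE = 0.0328, z = 3.35. With Zimura up 0.4 mm, the estimate is 0.07, SE = 0.0317, z = 2.21.

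**Tipping points (mm); missing shown as Zimura/Sham**

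| Effect | Missing | Both arms down | Zimura down | Sham down | Zimura up |
|---|---|---|---|---|---|
| 0.11 | 5%/5% | 2.18 | never | 0.91 | 0.91 |
| 0.11 | 10%/10% | 1.57 | never | 0.47 | 0.47 |
| 0.11 | 15%/10% | above 7 | never | 0.46 | 0.31 |
| 0.11 | 10%/15% | 0.69 | never | 0.31 | 0.46 |
| 0.08 | 5%/5% | 1.28 | never | 0.41 | 0.41 |
| 0.08 | 10%/10% | 0.90 | never | 0.20 | 0.20 |
| 0.08 | 15%/10% | above 5 | never | 0.19 | 0.13 |
| 0.08 | 10%/15% | 0.32 | never | 0.13 | 0.19 |

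At 15%/10% and effect 0.11 mm, a 0.4 mm shift down in both arms moves the estimate to 0.11 + 0.06 − 0.04 = 0.13 and z from 3.55 to 3.86.

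**What the adverse tips mean.** Growth in Zimura patients with missing data at the tipping point is (0.40 − effect + shift). Relative to Sham growth this is 3.0, 1.9 and 1.5 times at 5%/5%, 10%/10% and 15%/10% for effect 0.11, and 1.8, 1.3 and 1.1 times for effect 0.08.

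**What the written rule can overturn.** If lesions do not shrink, downward shifts stop at about 0.40 mm. For shifts from 0 to 0.40 mm, the significant results that can be lost are:

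| Missing | Both arms down | Zimura up |
|---|---|---|
| 5%/5% | starting p 0.041 to 0.05 | starting p above 0.0075 |
| 10%/10% | 0.035 to 0.05 | above 0.0008 |
| 15%/10% | none | above 0.00006 |

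The exception is 10%/15%, where shifting both arms down overturns starting p above 0.0055.

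**Alpha.** The SAP lowers alpha by an amount "equal to (two-sided) 0.001 for each DSMB meeting for any look at the data". With three such meetings assumed, alpha is 0.047 and the critical value 1.986. The adverse tips of 0.47 and 0.31 mm become 0.46 and 0.31 mm.

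**Visit-level check.** Square-root GA at 0, 6 and 12 months was simulated with multiple imputation under MAR within arm and a linear slope model (baseline mean 2.8, SD 0.6 and residual SD 0.1, all assumed). At effect 0.11 mm, both arms down tipped at 1.51 mm (10%/10%), 0.70 mm (10%/15%) and not up to 2.0 mm (15%/10%). Zimura up tipped at 0.45–0.48 mm (10%/10%) and 0.32–0.34 mm (15%/10%).

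**The case against.** The strongest reply is that the fault is the unnamed arm, because a downward shift is not lenient in itself. Shifting Sham alone downward tests the contrast as hard as shifting Zimura upward when missingness is equal (0.47 mm for both at 10%/10%). Shifting both arms down also works against the drug when Sham has more missing data: at effect 0.08 mm and 10%/15% it tips at 0.32 mm. This is correct, but the SAP specifies neither case. Whether the test is adverse would depend on a programming choice or on the pattern of dropout.

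Second, the SAP's analyses 3 and 4 already give Zimura patients with missing data the Sham mean, and analysis 3 falls within the stated robustness expectation. That deserves credit. It is one fixed penalty, though: adding 0.11 mm with a valid SE moves z only from 3.60 to 3.23 (10%/10%) or from 3.55 to 3.00 (15%/10%). It never goes worse than Sham. The pattern-mixture restrictions are not a graded shift either.

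Third, at the design effect the adverse tips need 1.5 to 3.0 times Sham growth, so a corrected analysis may also look robust. This stands. The adverse shift is modest only at smaller effects with 10–15% missing. The 0.40 mm bound comes from the no-shrinkage argument and does not say that so large an upward shift is plausible.

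Fourth, the no-shrinkage argument has limited support. Protocol 4.1 says "Geographic atrophy is a significant cause of bilateral, irreversible and severe loss of functional vision", which concerns vision and not measured lesion area. The bound is therefore an assumption about averages.

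Finally, the study-report appendix may state the arm and direction actually used. It is not among these documents and would not change what the SAP prespecified.

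**Conclusion.** The concern holds. Followed as written, the Year 1 rule moves missing values toward the better outcome in an unnamed arm, so a large tipping point is not evidence against worse outcomes in Zimura patients with missing data. With both arms shifted and a 0.11 mm effect, the written rule tips at 1.57 mm (10%/10%), against 0.47 mm for the adverse shift. With more missing on Zimura, it strengthens the result.

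The exact tipping points depend on the back-solved SD of 0.29 mm, the assumed missing rates and the square-root scale. The direction of the problem does not. It should be fixed, but the reach is limited: this is one of several sensitivity analyses, and the primary estimate, test and alpha do not depend on it.

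**What to change.** Replace the shift-imputation rule in the Year 1 SAP with text such as:

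> Missing square-root GA values will be imputed under MAR within arm. A shift d will then be added (larger GA) to the imputed values in the Zimura arm, with Sham unshifted. d will increase from 0 until significance is lost at the DSMB-adjusted alpha. The growth implied in Zimura patients with missing data at the tipping point will be compared with observed Sham growth. A two-way grid of arm-specific shifts will also be shown.

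In Year 2 SAP 4.2.1.3.2, state the same direction in the SAP itself, with EM and EOM as the shifted arms. Put the shift on the untransformed area scale set in 4.2.1.2, because a Year 1 shift in mm cannot be carried over to an area in mm².

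Section 1 of the Year 2 SAP says that the Year 1 primary analysis has been conducted, so any corrected Year 1 tipping-point analysis must be labelled post hoc.

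The cost is SAP wording and minor programming. The primary analysis does not change. The sensitivity result may be less favourable, and prespecification of the Year 1 version cannot be recovered.

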CONFIDENTIAL

Descriptive statistics will be tabulated as follows:

- Categorical data will be summarized in contingency tables presenting frequencies and percentages.
- Continuous data will be summarized using number of non-missing values (n), mean, standard deviation, median, minimum, 1st quartile (Q1), 3rd quartile (Q3), and maximum values.

Listings with individual subjects' data will be provided for all CRF (including derived data) and central laboratory data or other external data. Data collected in the CRF that are *not* present in a table will also be listed (e.g., time and method of tonometry, comments fields, data on Fatal Outcomes page, etc.).

Visit Windows

The scheduled visits will be used in the analyses over time.

Missing scheduled follow-up visits will be substituted by an unscheduled or early withdrawal visit occurring within each follow-up visit window, if there is only one unscheduled or early withdrawal visit occurring within the window. If there are multiple unscheduled or early withdrawal visits occurring within the window, the closest one within the visit window will be used. If no unscheduled or early withdrawal visit occurred within the window, the visit will be considered as missing. The *details* are tabulated in **Appendix 1**.

Procedures for Minimizing the Occurrence of Missing Data

Of note, the proper approach to address missingness is the prevention of missing data. The sponsor will implement aggressive proactive approaches to minimize the number of patients who are not assessed at 12 months. Among these approaches are the following:

- The study protocol properly distinguishes between reasons for nonadherence (that is, for not receiving randomized therapy and hence for being “off study treatment”) versus nonretention (that is, for not obtaining outcome information and hence for being “off study”). There are only 2 valid reasons a patient can be off study: withdrawal of consent or the achievement of all required efficacy and safety end point information
- The term ‘withdrawal of consent’ is used only when the patient no longer wishes to participate in the trial and no longer authorizes the investigators to make efforts to continue to obtain their outcome data
- Patients are educated during the informed consent process about the continued scientific relevance of their data even if they discontinue treatment, as well as the deleterious effect that missing data has on trial integrity and credibility

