A mixed model for repeated measures (MMRM) will be applied to all available data, using as response variable the square root of GA area measured by FAF in at least 3 time points: Baseline, Month 6, and Month 12. The MMRM will be used to assess the difference between the treatment groups in terms of the rate of growth of the square root of GA area (slope) over 12 months. Previous trial OPH2003 (GATHER1) showed the change in the square root of geographic atrophy to be remarkably linear over time. As a result, a linear model is not only convenient and easily interpretable, but it is also appropriate given the natural history of the disease. A model will be fitted by using restricted maximum likelihood (REML) and include Baseline VA (< 50 letters vs. ≥ 50 letters), and pattern of FAF at the junctional zone of GA (none/focal vs. banded/diffuse) as used in the randomization as covariates. For the model, fixed effects will include time, treatment, Baseline VA (< 50 letters vs. ≥ 50 letters), pattern of FAF at the junctional zone of GA (none/focal vs. banded/diffuse), treatment by time interaction, Baseline VA (< 50 letters vs. ≥ 50 letters) by time interaction, and pattern of FAF at the junctional zone of GA (none/focal vs. banded/diffuse) by time interaction. The model will include an unstructured modelling of within-subject correlations. If this analysis fails to converge, alternative structures (e.g., heterogeneous autoregressive, heterogeneous compound symmetry, autoregressive, or compound symmetry, in this order) will be considered. The Kenward-Roger approximation will be used to estimate denominator degrees of freedom. The test of difference between the two arms in the mean rate of growth

CONFIDENTIAL

(slope) of the square root of GA area over 12 months will be assessed by testing the appropriate contrast of the model parameter estimates.

[Redacted content]

CONFIDENTIAL

[Redacted text block]

[Redacted text line]

[Redacted text line]

[Redacted text line]

[Redacted text line]

[Redacted text line]

[Redacted text line]

[Redacted text line]

[Redacted text line]

[Redacted text line]

[Redacted text line]

[Redacted text line]

[Redacted text line]

[Redacted text line]

[Redacted text line]

[Redacted text line]

[Redacted text line]

[Redacted text line]

[Redacted text line]

[Redacted text line]

[Redacted text line]

CONFIDENTIAL

- █ [REDACTED]
- █ [REDACTED]
- █ [REDACTED]
- █ [REDACTED]
- █ [REDACTED]
- █ [REDACTED]
- █ [REDACTED]

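### With three FAF visits, CCMV and NCMV equal MAR for Month 12 given Baseline and Month 6, so this sensitivity analysis cannot show a loss of effect after the last image

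*SAP*

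**What the plan says.** The primary analysis (Year 1 SAP, Analysis of Primary Efficacy Outcome) is an MMRM on the square root of GA area, "measured by FAF in at least 3 time points: Baseline, Month 6, and Month 12". It uses observed data and relies on MAR. Under Sensitivity Analyses for Missing Data the SAP adds that, given MAR, "the model yields valid results that are comparable to those obtained by applying MI under the MAR assumption".

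The same section plans two groups of checks:

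- Four Miller imputations fill in observed means. The third gives the Sham mean to every patient with missing data. The fourth gives each arm the other arm's mean.
- Two multiple-imputation approaches, described as compatible with data missing not at random (MNAR), are introduced with the aim "To check the sensitivity of the results of the primary efficacy analysis" to the MAR assumption. One is a shift with a tipping point, where "it will be assumed that their expected value is smaller (shifted) by a specified amount". In the other, "missing values at Month 12 visit will be imputed by using the pattern-mixture-model restrictions", and "Complete-Case Missing Value (CCMV) and Neighbouring-Case Missing Value (NCMV) restrictions will be applied".

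No offset is attached to these two restrictions. The readable text does not say how a missing Month 6 value, or a non-monotone pattern, is handled in the pattern-mixture step.

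**The concern.** A sensitivity analysis for MNAR is useful only if its imputations can move away from MAR in the direction that matters. The estimand follows patients regardless of treatment discontinuation. For patients who leave the study, the obvious threat is therefore that the drug effect fades after the last FAF image. That is a departure in Month 12 given the observed history.

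With only three visits, CCMV and NCMV leave that conditional distribution exactly where MAR puts it. Agreement between these analyses and the MMRM is then largely built in for patients lost after Month 6. A report that cites the agreement as evidence of robustness to MNAR would claim more than was tested by this step.

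**Working it through.** **Inputs.** From the Year 1 SAP: three visits; about 400 patients, 1:1; effect 0.11 mm over 12 months; smallest significant estimate 0.057 mm at two-sided 0.05; power 97%. From the protocol (Study OPH2003): a 27.38% reduction, so Sham growth is 0.11/0.2738 = 0.402 mm. Not given: the SD and the rate of missing FAF. The SAP says only that steps will be taken to "minimize the number of patients who are not assessed at 12 months". The rates and departures below are assumptions.

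**1. The plan's own figure.** SE = 0.057/1.96 = 0.0291. With 200 per arm, SD = 0.0291/√(2/200) = 0.291 mm. Power = Φ(0.11/0.0291 − 1.96) = 96.6%, which agrees with 97%. At two-sided 0.01 it is 88.6%, in line with the SAP's statement of nearly 90%. This only sets the scale.

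**2. What each restriction uses as donor.** Take monotone patterns: P3 complete, P2 missing Month 12, P1 missing Months 6 and 12.

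| Distribution needed | CCMV | NCMV | MAR |
|---|---|---|---|
| Month 12 given Baseline, Month 6 (P2 and P1) | P3 | P3 | P3 |
| Month 6 given Baseline (P1 only) | P3 | P2 | P2 + P3 |

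The first row is the same throughout because only P3 has Month 12. For P2 the imputation is exactly MAR. For P1 it can differ, but only through the imputed Month 6 value. No assumed figure enters this step.

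**3. Size if Zimura leavers grow at the Sham rate after their last image.** A patient lost after Month 6 loses half the effect (0.055 mm), and one lost after Baseline loses all of it (0.110 mm).

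- 15% missing (12% + 3%): 0.110 − 0.12×0.055 − 0.03×0.110 = 0.100 mm
- 20% missing (split taken as 16% + 4%): 0.110 − 0.16×0.055 − 0.04×0.110 = 0.097 mm

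A simulation of 600 trials with 200 per arm and 5 imputations gave, at 15%, MAR 0.110, CCMV 0.111, NCMV 0.110, and 0.101 when missing Zimura values took Sham increments. At 20% the first three were all 0.110 and the last 0.096. The missed amount is 0.010 to 0.013 mm, or 9% to 12% of the effect.

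**4. Stress test.** One million patients per arm, with departures in the Zimura arm only and the same missingness in both arms. Departures of 0.20 to 0.50 mm exceed full loss of the 0.11 mm effect; they test the mechanism and are not plausible sizes. Entries in the last four columns are the 12-month treatment difference in mm.

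| Missing both / Month 12 only | Extra Month 6 growth in leavers | Further Month 12 departure | Truth | MAR | CCMV | NCMV |
|---|---|---|---|---|---|---|
| 0% / 10% | 0 | 0.20 | 0.0897 | 0.1097 | 0.1097 | 0.1097 |
| 5% / 5% | 0 | 0.20 | 0.0899 | 0.1100 | 0.1100 | 0.1101 |
| 5% / 5% | 0.05 | 0.20 | 0.0799 | 0.1054 | 0.1056 | 0.1015 |
| 10% / 10% | 0.05 | 0.20 | 0.0499 | 0.1009 | 0.1019 | 0.0935 |
| 10% / 10% | 0.10 | 0.20 | 0.0300 | 0.0917 | 0.0935 | 0.0769 |
| 10% / 5% | 0.10 | 0.50 | 0.0054 | 0.1011 | 0.1021 | 0.0856 |
| 0% / 20% | 0 | 0.50 | 0.0101 | 0.1103 | 0.1103 | 0.1103 |

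In every row, patients with Month 6 observed received the same imputed Month 12 mean under all three (first row: 0.29251 mm growth). Where only Month 12 departs, nothing moves by more than 0.0001 mm. Where leavers also differ at Month 6, NCMV moves from MAR by 0.0039 to 0.0155 mm and CCMV by at most 0.0018 mm, while MAR is off by 0.0255 to 0.0957 mm in those rows.

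**5. The neighbouring Miller analyses.** Assume that 12-month growth is the quantity filled in (the SAP says only observed means) and that missingness is equal by arm. The third then gives 0.85×0.110 = 0.094 and 0.80×0.110 = 0.088 mm. The fourth gives (1 − 2×0.15)×0.110 = 0.077 and (1 − 2×0.20)×0.110 = 0.066 mm.

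**The case against.** The strongest reply has four parts.

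- **CCMV and NCMV are not MAR.** A reader might infer that they simply reproduce the MAR analysis. That is too strong. For patients missing both post-baseline visits they are different restrictions on Month 6, and the difference carries into Month 12. This stands. In addition, the simulation in step 3 makes patients who leave after Month 6 look like completers up to that visit, so it could not have shown NCMV moving.
- **MNAR is tested elsewhere.** A reader might also infer that the SAP leaves departures from MAR untested. It does not. The third and fourth Miller analyses push against the drug, and in the scenarios of step 3 the third gives estimates below the true effect. The shift analysis has a free parameter. This stands in part. The Miller schemes fill in means with no stated conditioning on the patient's Month 6 value and no stated allowance for imputation uncertainty. The shift is worded only towards smaller growth and names no arm; applied to Zimura, smaller growth favours the drug.
- **Little is truly missing.** The SAP plans to follow patients after they stop treatment, an early-withdrawal visit includes FAF, and such a visit can replace a missing one within its window. Loss of effect in patients still observed already enters the MMRM. This stands and limits the point to values that are really absent.
- **The size is small and the analysis is only supportive.** This also stands.

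**Conclusion.** The point holds for Month 12 given the observed history. CCMV and NCMV as specified equal MAR there, so this analysis lacks the property that the SAP assigns to it for patients lost after Month 6. The identity needs only three visits, monotone dropout and no offset.

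The size rests on assumed dropout of 15% to 20% and growth at the Sham rate after the last image: about 0.010 to 0.013 mm. A reader might infer that the primary result is in danger. The figures do not support that for an effect near 0.11 mm, since 0.097 to 0.100 mm is far above 0.057 mm. Holding the SE fixed, a 9% to 12% loss would matter only for a significant MAR estimate below about 0.057/0.91 = 0.063 to 0.057/0.88 = 0.065 mm. The defect is confined to one of several sensitivity analyses and leaves the primary analysis as it is.

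**What to change.** CCMV and NCMV can stay, but the SAP should say that for patients with Month 6 observed they equal MAR at Month 12, and that their agreement with the MMRM is not evidence of robustness to MNAR.

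Add one of the following to the pattern-mixture step:

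- a reference-based multiple imputation, in which missing Zimura values after the last FAF take Sham-arm increments, Sham is imputed under MAR, and results are combined by Rubin's rules; or
- an arm-specific Month 12 offset towards larger growth in the Zimura arm, over a stated range.

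State also how a missing Month 6 value and non-monotone patterns are handled.

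The cost is SAP wording and some programming in the multiple-imputation procedure already named. The downside is a slightly less favourable sensitivity result. The Year 2 SAP (Section 1) records the Year 1 analysis as done, so an addition made now should be labelled post hoc; the caution on reporting applies either way.
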